1. INTRODUCTION

1.1. Study Purpose

Medtronic, is sponsoring a quality improvement study called Brady MX. It is hypothesized that lack of awareness of treatment and diagnostic pathways results in lower number of referrals to implanters of IPGs

- Education and process improvement initiatives can improve the diagnosis and increase appropriate therapy applications for SND
- The quality improvement methods to be studied will have general applicability which can be utilized beyond the Brady MX study.

1.2. Study Scope

The study may be conducted in up to 10 sites under oversight by the “Secretaria de Salud” in Mexico. The study will be conducted in two phases, with Phase I serving as control subjects and Phase II measuring the impact of the intervention. Up to 500 subjects will be enrolled in the study with at least 210 enrolled per phase. An enrollment target of 45 subjects per center in total is desired to make center-specific outcomes more meaningful and reliable in measuring changes in diagnostic rates and patient acceptance of indicated therapy. Centers that enroll faster than others will be allowed to enroll up to 42 subjects within each phase of the study.

All study subjects will be followed until the study exit criteria are met or until official study closure. Study closure is defined as closure of a clinical study that occurs when Medtronic and/or regulatory requirements have been satisfied per the Clinical Investigation Plan and/or by a decision by Medtronic or regulatory authority, whichever occurs first. The expected study duration from first enrollment to last follow-up, is approximately 26 months.

The aim of Brady MX is to improve adoption of consensus treatment guidelines in Mexico for SND indicated patients as described in the ACC/AHA/HRS guidelines² and ESC guidelines³. Implantable Pulse Generator (IPG) therapy has been integrated into the ACC/AHA/HRS guidelines and ESC guidelines without evidence from large randomized clinical trials (RCT). While the RCT is considered the gold standard for establishing that a therapy causes a clinical outcome effect, the scientific community is calling for clinical research beyond the RCT. A manuscript in Circulation in 2008¹² states that the external validity of RCTs must be supplemented by real world “effectiveness research”, including pragmatic studies, meta-analyses and observational trials. Guidelines and major publications help with awareness of what is possible when treating disease and an important component of adoption is the physician’s personal experience with the therapy. As such, the evidence in this study will provide personal experience, powerful information for the individual physician, and an aggregated analysis.

3. SYSTEM DESCRIPTION AND INTENDED USE

3.1. Device Description

Subjects meeting an ACC/AHA/HRS or ESC indication for pacing therapy may be implanted with any pacemaker from the Medtronic family of devices that are market released and any market released lead. There are no programming requirements for this study. All devices are used according to medical, technical and ethical standards without any change to the approved use of the device.

4. METHODOLOGY

The Brady MX study is a prospective, sequential, post market study with an educational phase and any market released pacemaker from the Medtronic family of devices may be used in this study. It is hypothesized that the use of a practice-specific process improvement intervention consisting of education, diagnostic algorithm(s) and

documentation tools that advocate and reinforce adherence to consensus treatment guidelines will improve the quality of care for patients with sinus node dysfunction (SND). The study will be conducted in two phases, with Phase I serving as control subjects and Phase II measuring the impact of the intervention.

The study will be conducted in compliance with the Clinical Investigation Plan, Clinical Trial Agreement, approved labeling, latest version of the Declaration of Helsinki, and laws and regulations of the country in which the study is conducted, including data protection laws.

Principles of the Declaration of Helsinki have been incorporated into this study by means of the patient informed consent/Patient Data Release process, IRB/MEC approval (if required); study training, clinical trial registration, risk benefit assessment, and publication policy, etc.

The study may enroll up to 500 Mexican subjects. with at least 210 subjects enrolled per study phase. Once enrolled, Phase I subjects should be followed for approximately 6 months and Phase II subjects should be followed for approximately 6 months. Brady MX is anticipated to be completed in mid-2018.

Subject data will be collected at enrollment/baseline, diagnostic assessment visits and implant visit. Data will continue to be collected until one of the exit criteria has been met. Brady MX does not mandate specific requirements regarding any other procedures, subject visits to the clinic, clinical treatment of subjects or device programming. Clinical data will be collected using electronic case report forms.

Centers will be eligible to enroll subjects in Brady MX upon Medtronic's receipt of required center activation materials and written approval.

4.1. Study Objectives

Primary Objectives

1. Evaluate the impact of the intervention on the diagnosis of SND
2. Evaluate the impact of the intervention on SND subjects receiving a referral for an indicated IPG device

Secondary Objective

The secondary objectives to be measured include:

1. Evaluate the impact of the intervention on whether SND subjects undergo an IPG implant

Ancillary Objectives

1. Characterize the patient population that declines indicated IPG therapy
2. Characterize the usage and impact of interventional tools (e.g., diagnostic algorithm(s), patient education tools) on the management of SND
3. Evaluate device pacing mode of subjects receiving indicated IPG device before and after intervention
4. Characterize the impact of the intervention on screening strategies and the impact on enrollment.

4.2. Subject Selection

Subjects of both genders meeting all the inclusion criteria and none of the exclusion criteria are eligible for the study.

Inclusion Criteria:

- Patient is at least 18 years of age
- Patient's heart rate meets at least **one** of the following:
 - Patient has a sinus rate ≤ 50 **OR** a junctional escape rhythm no faster than 50
 - Patient has a history of exercise intolerance
- Patient complains of general fatigue, shortness of breath, shortness of breath with exertion, syncope, light headed dizziness, palpitations, lethargy, dyspnea **OR** malaise within the last 30 days that are not related to other discovered causes (such as untreated hypothyroidism or anemia).
- Patient (or patient's legally authorized representative) is willing and able to sign and date written Patient Consent Form/Patient Data Release Consent

Exclusion Criteria:

[figure not shown]
- Patient has recent history of blood loss
- Patient has a medical history leading to suspicion of neurological disorder
- Patient has a history of Chronic Atrial Fibrillation
- Patient is enrolled or planning to participate in a concurrent drug and/or device study at any time during the course of this clinical study without documented pre-approval from the Medtronic study manager
- Patient is not expected to survive for 12 months
- Patient is anticipated to be unwilling or unable to comply with the clinical investigation plan

Subjects will be screened to ensure they meet all of the inclusion and none of the exclusion criteria. Subjects are considered enrolled upon signing the Informed Consent Form/Patient Data Release.

4.3. Study Design

There are two phases for Brady MX

Figure 1: IMPROVE Brady Study Design

Phase I: This phase of the study serves as a control period. During Phase I physicians will assess and treat subjects per their site’s standard care practice.

Enrollment for Phase I is anticipated to occur for approximately 6 months but will continue until a minimum of 210 subjects have been enrolled. For subjects enrolled during Phase I, collection of diagnostic assessment and implant data will be complete 6 months after the last enrollment. At that time, all Phase I subjects will be exited

Phase II:
The objective of the Brady MX study is to provide investigators with comprehensive resources that may be adapted by the Principal Investigator and his/her colleagues to create a practice specific process improvement intervention to improve the quality of care for patients.

At the completion of Phase I, the Principal Investigator and co-investigators will complete an educational workshop and be given access to the Brady MX toolkit. In addition, the Principal Investigator and his/her colleagues are encouraged to adapt tools from the Brady MX toolkit to create a practice specific process improvement intervention.

Immediately following completion of the educational workshop, study investigators will receive written authorization from Medtronic that they are authorized to enroll subjects in Phase II. Enrollment during this phase is anticipated to occur for approximately 6 months but will continue until a minimum of 210 subjects have been enrolled.

The Brady MX process improvement intervention toolkit may include an education workshop, diagnostic algorithm(s), patient video and tools for investigators to educate their patients on their disease state, available therapy options, and benefits and risks associated with the therapy options.

For subjects enrolled during Phase II collection of diagnostic assessment data will be complete 6 months after last enrollment. At that time, any subjects without a diagnosis will be exited from the study.

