4.4. Minimization of Bias

Potential sources of bias in this study may result from the Hawthorne effect, selection of study centers, selection of subjects, treatment of subjects, and evaluation of study data. The following methods have been incorporated into the study to minimize potential bias.

- Center selection criteria, documented under separate cover, will need to be met prior to participation in Brady MX. Study center characteristics will be collected at activation on possible differences that may affect the primary endpoints. Centers will be used as their own control
- Subjects will be screened to confirm eligibility with the help of screening logs, for enrollment with defined inclusion/exclusion criteria prior to enrollment
- Subject demographics will be collected at baseline on possible differences that may affect the primary endpoints
- It is anticipated that the distribution of subjects with various co-morbidities will vary by study centers. To minimize potential bias, all sites will be encouraged to enroll at least 5 subjects in each study Phase and enrollment at a site cannot exceed 42 subjects per phase to ensure a more even distribution of data
- All study Clinicians will be required to follow the Clinical Investigation Plan
- All study clinicians and Medtronic personnel will be trained on their respective aspects of the clinical investigation plan using standardized training materials.

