11.1. Primary Objective(s)

Primary Objective #1

Evaluate the impact of the intervention on the diagnosis of SND.

Hypothesis

The primary objective will be tested with the following hypothesis:

$$H_0: p_{1t} = p_{2t}$$

$$H_A: p_{1t} \neq p_{2t}$$

where p_{1t} is the proportion of patients with SND in Phase I and p_{2t} is the proportion of patients with SND in Phase II at time point t .

Endpoint Definition

The absolute change in the proportion of subjects diagnosed with SND at pre-specified time points ($\% = \text{number diagnosed} / \text{number enrolled} \times 100$ at time point $t = 6$, or t is a multiple of 6 representing any additional 6-month interval for which there is sufficient follow-up information) and the absolute change in the number of subjects diagnosed with SND per person-year.

Analysis Methods

A. Statistical Methodology

To compare the proportion of subjects with an SND diagnosis pre-intervention (Phase I) to the proportion post-intervention (Phase II), a binomial exact test will determine statistical significance. The proportion of subjects diagnosed will be evaluated at multiple time points because the time to diagnosis is expected to vary by hospital. Thus, times are pre-specified starting at 6 months and any additional 6-month interval thereafter for which there is sufficient follow-up data available to compare study phases. Proportions calculated at all available time points will be reported. Additionally a Poisson regression will compare the average number of subjects with an SND diagnosis in Phase I and Phase II where the subject time in study is treated as an offset in the model. The above described tests will be performed separately within site as well as overall.

B. Determination of Patients/Data for Analysis

All subjects that are enrolled in the study and that meet study inclusion/exclusion criteria will be included in the determination of the proportion estimates. The proportion estimates will be calculated based on information from fixed time points at 6 months of follow-up, and any additional 6-month interval thereafter for which there is sufficient follow-up data available to compare study phases. The number of subjects that obtain a SND diagnosis by pre-specified time point t is included in the numerator and the number of subjects enrolled is included in the denominator.

Sample Size Methods and Assumptions

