The proportion of SND diagnoses in subjects with bradycardia is currently unknown. The power calculations conservatively assume that the SND diagnosis will be 10% at six months of follow-up, or equivalently an SND incidence of 0.2 diagnoses per person-year. If 200 subjects are collected each in Phase I and in Phase II, assuming a type I error of 0.05 and power of 0.80, a binomial exact test will detect an increase in SND diagnosis of at least 10%. For example, the study will find a statistically significant difference between a Phase I SND percentage of 10% at 6 months and a Phase II SND percentage of 20% at 6 months. If the proportion of SND diagnoses is smaller than 10%, there will be more power to detect significant differences in the diagnosis proportion. It is expected that the study attrition rate may be 5% of the study population. To account for attrition, the sample size for Phase I will be a minimum of 210 subjects and for Phase II will be a minimum of 210 subjects.

Primary Objective #2

Evaluate the impact of the intervention on SND subjects receiving a referral for an indicated IPG device.

Hypothesis

The primary objective will be tested with the following hypothesis:

$$H_0: p_{1t} = p_{2t}$$

$$H_A: p_{1t} \neq p_{2t}$$

where p_{1t} is the proportion of patients referred for an IPG in Phase I and p_{2t} is the proportion of patients in Phase II at time point t .

Endpoint Definition

The absolute change in the proportion of subjects receiving therapy referral for an indicated IPG at pre-specified time points ($\% = \text{number receiving IPG}/\text{number with SND diagnosis} \times 100$ at time point t where $t = 3, 6$, and any additional 3-month interval for which there is sufficient follow-up information) and the absolute change in the number of subjects implanted per person-year.

Analysis Methods

Statistical Methodology

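### Phase II patients are chosen after the workshop, and Primary Objective #1 compares crude proportions, so a change in who is enrolled can mimic or mask a change in diagnosis

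*Combined protocol and SAP*

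**What the plan says.** **Order of events.** Phase I is a control period under each site's usual care. When it ends, the investigators take the workshop and receive the toolkit. Section 4.3 continues: "Immediately following completion of the educational workshop, study investigators will receive written authorization from Medtronic" that they may enroll Phase II subjects.

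**Discretion.** Under section 5.3 the investigator or coordinator assesses eligibility, and inviting an eligible patient is optional. Enrollment can take place at any time once the criteria are met. No rule requires consecutive enrollment.

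**Breadth of entry.** In section 4.2 the heart-rate criterion is met by a sinus rate of 50 or less, by a junctional escape rhythm no faster than 50, or by this alternative: "Patient has a history of exercise intolerance". A recent symptom, which may be as non-specific as fatigue or malaise, is also needed. The sample-size text in 11.1 nevertheless speaks of bradycardia: "The proportion of SND diagnoses in subjects with bradycardia is currently unknown".

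**Safeguards.** Section 4.4 lists selection of subjects among the possible biases. Its measures are defined criteria, screening logs, centers as their own control, a cap of 42 per site per phase, and baseline data: "Subject demographics will be collected at baseline on possible differences that may affect the primary endpoints". Ancillary Objective #4 is to "Characterize the impact of the intervention on screening strategies and the impact on enrollment". Section 11.3 analyses it descriptively, as the share enrolled of those screened at each site.

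**Primary analysis.** For Objective #1, those diagnosed by time t form the numerator and "the number of subjects enrolled is included in the denominator". The phases are compared by a binomial exact test, with a Poisson regression that uses time in study as offset. Both are run within site and overall. No baseline covariate or patient-level stratum is named.

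**The concern.** Objective #1 asks whether the intervention changed the diagnosis of SND. The crude proportion can move for two reasons: a given patient is more likely to be diagnosed, or the patients enrolled are more (or less) likely to have SND. Because training comes before selection, and the criteria admit quite different patients, the second reason cannot be set aside.

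The listed safeguards do not separate the two. Common criteria leave both entry routes open. The site cap and own-control comparison deal with differences between sites; this is a change over time within a site, so the within-site tests carry the same bias. An enrolled/screened ratio shows how many were taken, not who they were. The baseline data could help, but no primary analysis uses them.

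At stake is the meaning of the main result. A rise in yield per enrolled patient could be reported as better diagnosis, or a real improvement could be diluted by a wider intake.

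**Working it through.** **1. The plan's own figure.** The inputs in 11.1 are "assuming a type I error of 0.05 and power of 0.80", and "a Phase I SND percentage of 10% at 6 months and a Phase II SND percentage of 20% at 6 months", with a two-sided alternative. The pooled normal formula gives

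n = [1.960·√(2·0.15·0.85) + 0.842·√(0.10·0.90 + 0.20·0.80)]² / 0.10² = (0.990 + 0.421)² / 0.01 ≈ 199 per phase.

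The plan states 200, at which power is 80.2%. Adding 5% gives 200 × 1.05 = 210, as stated. The sample size reproduces, but it takes the two phases to enroll comparable patients.

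**2. Effect of a change in mix alone.** The documents give no SND rate by entry route, so these inputs are assumptions. Let r₁ be the six-month SND diagnosis rate in those entering with a rate of 50 or less or a junctional rhythm, r₂ the rate in those entering on exercise intolerance only, and m the share in the first group. Phase I has m = 50% and 10% overall, matching the plan. Rates within each route are the same in both phases, so the intervention has no effect on any patient. Then

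p(Phase II) = m·r₁ + (1 − m)·r₂.

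For example, m = 75% with 16%/4% gives 0.75 × 0.16 + 0.25 × 0.04 = 13%.

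The rejection probability is the sum, over all pairs of counts with 200 per phase, of the two binomial probabilities for those pairs where the two-sided Fisher p-value is at most 0.05.

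| r₁ / r₂ | Phase II share m | Phase II rate | False rejection |
|---|---|---|---|
| any | 50% (no shift) | 10% | 3.4% |
| 16% / 4% | 60% | 11.2% | 4.8% |
| 18% / 2% | 60% | 11.6% | 5.8% |
| 12% / 8% | 75% | 11.0% | 4.4% |
| 13% / 7% | 75% | 11.5% | 5.6% |
| 16% / 4% | 75% | 13.0% | 12.1% |
| 16% / 4% | 90% | 14.8% | 25.8% |
| 18% / 2% | 75% | 14.0% | 19.0% |
| 18% / 2% | 90% | 16.4% | 41.8% |

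The no-shift value is below 5% because Fisher's test is conservative.

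**3. The other direction.** Suppose the intervention truly doubles diagnosis in both routes (16% to 32%, 4% to 8%) while m falls from 50% to 25%. Phase II shows 0.25 × 0.32 + 0.75 × 0.08 = 14%. The chance of rejection is 19.0%, against 76.8% for the same test at 10% versus 20% with no shift.

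**4. Would stratifying help?** Take assumed strata with SND in 30% and 5%, unchanged by the intervention, and let the high-rate share rise from 20% to 40%. The Phase II rate is 0.40 × 0.30 + 0.60 × 0.05 = 15%, and the crude test rejects in 27.6% of trials. A Cochran-Mantel-Haenszel test on the same strata rejects in about 5% (40,000 simulated trials). This protection exists only if the stratifying variable is measured.

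**The case against.** The strongest reply concerns adjustment itself. In Phase II, entry route, recorded heart rate and elicited symptoms are all observed after the workshop. A trained investigator may document a rate of 50 or less in a patient who would have entered Phase I on exercise intolerance alone. That is better detection, and adjusting for entry route would remove part of it as if it were confounding. This stands. A reader might infer that the adjusted estimate should replace the crude one as the basis for the claim; the plan's data flow does not support that.

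Second, modest shifts, or modest differences between routes, leave the error rate near nominal, as the table shows. This also stands. A reader might take 42% as the trial's false-positive rate; it is the far end of an assumed range.

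Third, a reader might infer from Ancillary Objective #4 that the sponsor expects selection to change. The text only plans to describe any impact on screening and enrollment. It shows that the possibility was recognized, not that a shift was predicted.

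Fourth, section 4.4 does more than collect demographics: it has screening logs, fixed criteria, a site cap and own-control centers. These are real but partial. None corrects a within-site change in patient mix.

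**Conclusion.** The concern holds as a gap in the analysis plan. Selection follows training, it is discretionary, the entry criteria are broad, and the primary comparison has no adjustment for patient mix. A crude difference therefore cannot by itself be attributed to better diagnosis, nor its absence to lack of effect.

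The size and direction of any bias are unknown. With 200 per phase and a two-sided Fisher test, false rejection is about 4–6% for modest shifts, and 12–42% when the bradycardic share moves from 50% to 75–90% with routes that differ fourfold or ninefold, against 3.4% with no shift. These figures rest on assumed route rates and an assumed 50/50 split in Phase I. The documents do not show that a shift will occur. The point should be settled before the data are seen, because covariates chosen afterwards would carry little weight.

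**What to change.** In 11.1, Objective #1:

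- Keep the crude exact test and prespecify beside it one adjusted or stratified phase comparison, reported as a risk difference. Start with site and age, which training does not alter in a given patient. As a second step add entry route (rate 50 or less or junctional rhythm, versus exercise intolerance only).
- State that a conclusion of improved diagnosis requires the crude and adjusted risk differences to be consistent, and define consistent in advance. Otherwise report the result as a change in yield per enrolled patient.
- Tabulate baseline characteristics and entry route by phase next to the screening-log result of Ancillary Objective #4.
- Make sure the case report form records which heart-rate sub-criterion was met. Table 1 has an inclusion/exclusion row, but Appendix B says the forms were still in development, so this cannot be assumed.

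**Cost.** SAP wording, one further model, one table and possibly one form field. Design and sample size do not change, since the exact test stays. Table 1 already lists demographics, symptoms and heart rate at baseline.

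**Limits.** On the plan's rates about 20 and 40 events are expected (200 × 10% and 200 × 20%), so covariates must be few. The entry-route step may remove some genuine detection effect. Clinical suspicion that is not recorded remains unadjusted.
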